7.4.7 Handling of Early Termination Visits and Additional Treatments

Early termination visit data for safety variables (on or prior to Day 29) and for immunogenicity variables (on or prior to Day 181) will be analyzed at the closest scheduled visit. If the closest visit has valid data, the early termination data will be assigned to the next available visit.

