3	1×10^{11}	15	5
Study Total Target		45	15
Total		60	

A sentinel group of 5 subjects from each cohort will be dosed. Dosing of the remainder of each cohort may proceed after the last sentinel subject completes Day 8 if no events meeting stopping criteria have occurred. The Safety Review Committee (SRC), consisting of the Investigator, the Medical Monitor, and a Sponsor Representative, will review AE, reactogenicity, and laboratory data through at least Day 8 for all subjects in each cohort before subjects are randomized to the next higher dose. If any event meeting stopping criteria occur, the SRC will review all available safety information before additional patients are dosed. Stopping criteria are as follows, using the Food and Drug Administration (FDA) toxicity grading scale [1]:

- Occurrence of any related SAE or Grade 4 AE
- Occurrence of 2 Grade 3 AEs in the same organ system
- Occurrence of the same Grade 3 laboratory abnormality in 2 or more subjects

Each subject will record local events, systemic events, and oral temperature in a diary daily for 14 days after the NasoVAX/placebo dose. Each subject will be contacted by telephone on Day 2 for safety assessment and review of the diary. Subjects will return to the investigational site on Days 4, 8, 15, 29, 91, and 181 for safety and immunogenicity assessments.

A serum sample will be collected from each subject for evaluation of influenza HAI assay against A/California/04/2009 predose on Day 1 on Days 4, 8, 15, 29, 91, and 181; Ad5 antibody, MN assay against both A/California/04/2009(H1N1) and nonrepresented strains, and HAI against nonrepresented strains will also be evaluated at Days 1 and 29. A whole

blood sample will be collected from each subject and processed to isolate PBMCs for evaluation of T-cell responses by ELISpot predose on Day 1 and on Day 8.

A nasopharyngeal swab sample will be collected from each subject at Screening and on Days 4, 8, 15, 29, and 91 to measure concentration of the Ad5 vector for assessment of vaccine vector shedding by quantitative polymerase chain reaction (qPCR) assay. Once a negative result is obtained, later samples may not be tested. ELISA for measurement of IgA will also be performed on the swab samples from Screening and Day 29 for evaluation of mucosal immune response.

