All AEs and medications will be recorded from signing of the informed consent form to Day 29. Thereafter to the end of the study, only MAEs, NCIs, SAEs, immunosuppressive medications (see list in Appendix 3), and vaccines will be recorded. Samples for clinical laboratory tests (hematology, serum chemistry, urinalysis) will be collected at Screening and on Days 8 and 29. A complete physical examination and vital signs will be performed at Screening and predose on Day 1, and targeted and symptom-driven physical examinations will be performed and vital signs measured 2 hours postdose and on Days 4, 8, 15, and 29. An electrocardiogram (ECG) will be performed at Screening and on Day 29. If a subject experiences acute symptoms compatible with adenoviral infection within 28 days after the NasoVAX/placebo dose, a sample will be collected for viral culture as clinically indicated.

One interim analysis of humoral immunogenicity data and safety data (including summaries of AE, reactogenicity, concomitant medications and vaccines, vital signs, ECG, and laboratory data and listing of any viral culture results) will be conducted when all data through the Day 29 visit is available and monitored for all subjects.

A complete schedule of procedures and assessments for study ALT-103-201 is in Table 4-2.

ALT-FLZ-401, Extent and Durability of Immune Response Following Seasonal Influenza Vaccination in Healthy Volunteers, was an open label study designed to generate an immunogenicity sample set similar to that of ALT-103-201 in subjects receiving a licensed influenza vaccine based on the same H1 strain (A/California 2009). The seasonal vaccine H1 component changed at the time of the ALT-103-201 study to A/Michigan, so it was logistically much easier to conduct this study non-contemporaneously with the seasonal vaccine licensed for use in 2016-17. The same site, entry criteria and schedule of assessments for immunogenicity were followed. Twenty subjects were enrolled and samples from this study were frozen and stored and then shipped to blinded laboratory for immunogenicity testing in parallel to the samples from ALT-103-201. The schedule of events for ALT-FLZ-401 is in Table 4-3.

Table 4-2. ALT-103-201 TIME AND EVENTS SCHEDULE

Study Visit	Screening	Dosing Period							Follow-up Period	
		Day 1		Day 2 ^a	Day 4	Day 8	Day 15	Day 29	Day 91	Day 181
Window (days)	Day -28 to Day -1	Predose	Postdose		± 1	± 1	± 1	± 3	± 10	± 10
Informed consent	X									
Demographics	X									

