- **Per-protocol (PP) Population:** All ALT-103-201 subjects in the Safety Population that received the assigned dose of the test article in accordance with the protocol; have HAI assay results on Days 1 and 29; and had no major protocol deviations affecting the primary immunogenicity outcomes as determined by the Sponsor prior to database lock. ALT-FLZ-401 subjects are included if they received the assigned dose of the test article in accordance with the protocol and have HAI assay results on Days 1 and 29. The PP Population is the primary population for immunogenicity analyses and will be presented regardless of whether subjects are excluded. The PP population will be analyzed as randomized.

SUMMIT ANALYTICAL

6 Analysis Variables

In what follows, variables to be analyzed have been grouped under the headings 6.1 to 6.4. Additional variables may be added as further drafts of the eCRF and this SAP are developed and/or as discussion unfolds concerning the usefulness of *derived* variables formulated using the information presented below.

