8.6 Immunogenicity Analysis

All immunogenicity analyses will be conducted on the PP Population. Analyses based on the ITT Population will be undertaken and presented only if >5% of subjects in any 1 dose group were excluded from the PP Population. Summaries and analysis will be completed by dose group and overall for subjects on an active NasoVAX dose.

The variables that will be analyzed, and the endpoints generated for each variable, are listed in Table 8-1:

Table 8-1. Immunogenicity Variables and Endpoints

Variable Name	GMT	GMR	SPR	SCR	Responder Rate	Geometric Mean SFUs	Compare to ALT-FLZ-401
A/California 2009 antibody level measured by HAI in serum	X	X	X	X			X
A/California 2009 antibody level measured by MN in serum	X	X			X		X
Cellular response to A/California 2009 peptides measured by enzyme-linked ELISpot in PBMCs					X	X	X
IgA antibody level measured by ELISA in nasopharyngeal swab	X	X					X
Antibody level measured by HAI in serum against the following nonrepresented strains: - A/Brisbane/59/2007 (H1 strain) - A/Saint-Petersburg/61/2015 (H1 strain) - A/New Jersey/76 (H1 strain) - A/Perth/16/2009 (H3 strain) - A/Vietnam/1203/2004XPR8 (H5 strain)	X	X			X		X
Antibody level measured by MN in serum against nonrepresented strains	X	X			X		X
Ad5 antibody levels in serum	X	X			X		

Note: Refer to Section 3 for descriptions of each endpoint.

Assay data will be tabulated by visit using the applicable endpoint(s) (e.g., GMT, GMR, or geometric mean SFUs) and their 95% CIs. Graphical representations of the longitudinal immune responses will also be given.

[figure not shown]
Analysis of covariance (ANCOVA) will be used in the analysis of the antibody levels at each post-baseline visit, with log-transformed antibody level as dependent variable, dose group as a factor, and baseline log-transformed level as a covariate. This model will be generated using SAS Proc Mixed with dose group in the CLASS statement and visit in the BY statement. Comparisons of post-baseline log-transformed antibody level will be conducted for each NasoVAX dose group against the placebo group and against the Fluzone group, if applicable. Least square (LS) means and 95% CI of the LS means of dose group, difference of LS means and 95% CI of the difference in LS means will be

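### SAP 7.4.7 moves early-termination sera to later visits with no limit on distance, so a Day 92 serum can be analysed as Day 181

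*SAP*

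**What the plan says.** SAP 7.4.7 covers early-termination data for immunogenicity variables up to Day 181. Such data go to the closest scheduled visit. If that visit is already filled: "If the closest visit has valid data, the early termination data will be assigned to the next available visit". Neither 7.4.7 nor any other part of the SAP sets a maximum distance or an analysis window. The windows in SAP Tables 4-2 and 4-3 are for scheduling visits, and 7.4.7 does not refer to them.

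SAP Section 4 schedules serum for "evaluation of influenza HAI assay against A/California/04/2009 predose on Day 1 on Days 4, 8, 15, 29, 91, and 181". The other serum assays are limited to two visits: "HAI against nonrepresented strains will also be evaluated at Days 1 and 29", and the same sentence covers microneutralization and Ad5 antibody. For ALT-FLZ-401 it states: "The same site, entry criteria and schedule of assessments for immunogenicity were followed". The Day 29 scheduling window nevertheless differs, at ±3 days in ALT-103-201 (Table 4-2) and ±1 day in ALT-FLZ-401 (Table 4-3 and Protocol Table 15.2). Both studies use ±10 days at Days 91 and 181.

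The visit label decides which analysis a sample enters. SAP 8.6 tabulates assay data by visit, and "Analysis of covariance (ANCOVA) will be used in the analysis of the antibody levels at each post-baseline visit". For ALT-103-201, per-protocol subjects must "have HAI assay results on Days 1 and 29; and had no major protocol deviations affecting the primary immunogenicity outcomes". ALT-FLZ-401 subjects need the same two HAI results but face no deviation criterion (SAP Section 5), and SAP 8.3 says their deviations were not collected.

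**The concern.** Under this rule a relabelled serum enters the Day 91 or Day 181 GMT, seroprotection rate and ANCOVA as if it had been drawn on time. Durability is in the title of ALT-FLZ-401, and these two visits are the ones that measure it. If titres fall over time, a serum drawn early usually makes the late response look better than it was. The rule in effect carries an earlier value forward, which sits poorly with the statement in SAP 7.4.8 that missing data are not imputed beyond values below the quantification limit.

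A second effect arises at Day 29. A subject who leaves soon after a valid Day 15 sample can have the termination serum counted as Day 29, and so can meet the per-protocol requirement without a sample near that day.

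**Working it through.** The plan gives no figure on this point to reproduce. The check applies the rule to each possible termination day and then sizes the effect.

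**Where a sample goes.** Inputs: serum visits at Days 1 (predose), 4, 8, 15, 29, 91 and 181 (SAP Section 4, Protocol Synopsis). Every earlier visit is taken as held on its nominal day with a valid sample. The next available visit was read both as the next empty visit in sequence and as the nearest empty visit; the two readings agreed on every day tried.

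| Serum drawn | Analysed as | Largest gap (days) | Outside the scheduling window |
|---|---|---|---|
| Days 16–28 | Day 29 | 29 − 16 = 13 | Days 16–27 (±1, ALT-FLZ-401); Days 16–25 (±3, ALT-103-201) |
| Days 30–90 | Day 91 | 91 − 30 = 61 | Days 30–80 (±10), 51 of 61 days |
| Days 92–180 | Day 181 | 181 − 92 = 89 | Days 92–170 (±10), 79 of 89 days |

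These are counts of calendar days, not probabilities.

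Two variants:
- If the Day 91 visit is held on Day 81, as its window permits, a Day 82 serum becomes Day 181: 181 − 82 = 99 days early.
- If Day 91 is missed, the midpoint (91 + 181)/2 = 136 sends sera from Days 92–135 to Day 91, up to 135 − 91 = 44 days late. The error then runs the other way.

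**Data path.** In ALT-FLZ-401 a serum is drawn at termination whichever protocol passage is followed, because the Day 29 and Day 181 procedures both include the 10-mL immunogenicity sample (Protocol 6.3.1). A subject who leaves after Day 29 stays in the per-protocol population.

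**Size.** This needs a titre half-life *h*, which the documents do not give; the assumed range is 365 to 60 days. The individual titre is misread by f = 2^(gap/h), and one such subject among n multiplies the GMT by f^(1/n).

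| Case | Gap (days) | f, h = 365 / 60 | GMT change, n = 20 |
|---|---|---|---|
| Day 100 as Day 181 | 81 | 1.17 / 2.55 | +0.8% / +4.8% |
| Day 92 as Day 181 | 89 | 1.18 / 2.80 | +0.9% / +5.3% |
| Day 82 as Day 181 | 99 | 1.21 / 3.14 | +0.9% / +5.9% |
| Mean over Days 92–180 | 45 | 1.09 / 1.68 | +0.4% / +2.6% |
| Mean over Days 30–90, as Day 91 | 31 | 1.06 / 1.43 | +0.3% / +1.8% |
| Day 135 as Day 91 (Day 91 missed) | −44 | 0.92 / 0.60 | −0.4% / −2.5% |

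In a 15-subject NasoVAX group the Day 100 case gives +1.0% to +6.4%.

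- **Subjects needed for a 10% rise at an 81-day gap:** 20 × ln(1.1)/ln(f) = 12.4 at h = 365 and just over 2.0 at h = 60, so 13 or 3 whole subjects.
- **Precision of the GMT:** the 95% CI factor at n = 20 is 10^(2.093 × SD/√20). With an assumed log10 SD of 0.3 to 0.6 this is ×/÷1.38 to ×/÷1.91.
- **Seroprotection:** one subject in 20 moves the rate by 5 percentage points, but only if the true titre crosses 1:40. A Day 100 titre of 40 has an expected Day 181 value of 40/1.166 = 34 to 40/2.549 = 16, or 0.22 to 1.35 two-fold dilutions lower. This matters mainly if waning is fast.

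**The case against.** The strongest reply is that this is small and may never arise. The 89-day gap requires a subject to attend Day 91 and leave the next day; averaged evenly over Days 92–180 the gap is 45 days, which roughly halves the effect of the Day 100 case. One subject's shift lies well inside the confidence interval of the GMT. The half-life is assumed, and the number of early terminations is not given; ALT-FLZ-401 is described as already enrolled, so its count may be zero. The rule is the same in every group, so between-group ratios are biased only if termination or waning differs. Durability is in the title of ALT-FLZ-401 but not in its listed objectives or endpoints, and in the SAP HAI is secondary and the Fluzone comparison exploratory. All of this stands, and it limits the severity.

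A further reply is that dropping these sera has its own cost: the late GMT then describes only subjects with a usable sample at that visit, and selection bias may remain. That is fair, and the percentages above compare relabelling with the unobserved true titre, not with dropping the subject. The fix is also uneven, since a late scheduled sample outside its window would still be analysed while a termination sample from the same day would only be listed.

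None of this supplies a distance limit or makes a Day 92 serum a Day 181 observation. Listing all immunogenicity data (SAP 8.6) lets a reader find such a sample but does not take it out of the analysis.

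**Conclusion.** The concern holds and is minor. As written, SAP 7.4.7 puts mistimed sera into the by-visit HAI summaries and models: up to 61 days early at Day 91 and 89 days early at Day 181 with visits on nominal days, and up to 99 days early within the permitted windows. These gaps follow from the documents alone.

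The effect on results rests on the assumed half-life of 365 to 60 days and on at least one early termination. It is then roughly 0.4 to 5.9% on a 20-subject Day 181 GMT per relabelled subject, usually upward. Late-visit error is confined to A/California HAI, the only immunogenicity assay scheduled at Days 91 and 181. The Day 29 effect on per-protocol membership has less protection in ALT-FLZ-401 than in ALT-103-201, where the major-deviation review could remove the subject.

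**What to change.** For immunogenicity variables, replace the rule in SAP 7.4.7 with:

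> An early-termination sample is analysed at a visit only if that visit has no valid sample and the early-termination sample was drawn within the analysis window, which is the same for both studies (±1 day at Days 4, 8 and 15, ±3 days at Day 29, ±10 days at Days 91 and 181); otherwise it is listed only. An early-termination sample counts as the Day 29 result for the PP Population only under this rule.

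These are analysis windows. Protocol visit windows do not change, and scheduled samples face no new test. At Day 29 the common window is wider than the ±1 day scheduling window of ALT-FLZ-401.

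The cost is two sentences and a check on collection dates in the visit derivation. There may be slightly fewer late observations and fewer per-protocol subjects. Losing one of 15 NasoVAX subjects is 6.7%, which exceeds the 5% trigger for the ITT analyses; one of 20 is exactly 5% and does not. Meeting the trigger only adds an analysis already planned.

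Separately, Protocol 6.4 disagrees with Protocol 4.3.1, 4.3.2 and Table 15.2 footnote g on which procedures apply to termination after Day 29. Those passages must be reconciled. The conflict does not itself bias titres, since a serum is drawn under each.

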7.4.8 Handling of Missing Values

Partial or Missing Dates

The following conventions will be used to impute missing portions of dates for AEs and concomitant medications. Note that the imputed values outlined here may not always provide the most conservative date. In those circumstances, the imputed value may be replaced by a date that will lead to a more conservative analysis.

A. Start Dates

- 1) If the year is unknown, then the date will not be imputed and will be assigned a missing value.
- 2) If the month is unknown, then:
 - i) If the year matches the first dose date year, then impute the month and day of the first dose date.
 - ii) Otherwise, assign 'January.'
- 3) If the day is unknown, then:
 - i) If the month and year match the first dose date month and year, then impute the day of the first dose date.
 - ii) Otherwise, assign the first day of the month.

B. Stop Dates

- 1) If the year is unknown, then the date will not be imputed and will be assigned a missing value.
- 2) If the month is unknown, then assign 'December.'
- 3) If the day is unknown, then assign the last day of the month.

Imputation

Any immunogenicity data that are below the limit of quantification will be imputed to one-half of the lower limit of quantification (LLOQ) for quantitative summary and analysis. For example, HAI values that are less than 10 will be imputed to 5. Otherwise, missing data will not be imputed.

7.4.9 Pooling of Investigator Centers

Not applicable since only 1 site each will be used for ALT-103-201 and ALT-FLZ-401.

7.4.10 Baseline Values

Baseline values are the values obtained prior to the vaccination on Day 1. If the baseline value is missing, the value at Screening will be treated as the baseline.

8 Summary of Study Data

For all summaries described below, subjects enrolled in the ALT-103-201 and randomized to an active dose will be summarized/listed under the heading "NasoVAX", while subjects enrolled in ALT-FLZ-401 will be summarized/listed under the heading "Fluzone".

8.1 Subject Disposition and Dosing Summary

The tabulation of number of ALT-103-201 and ALT-FLZ-401 subjects from in each dose group and overall for subjects on an active NasoVAX dose will be displayed for all subjects who are enrolled, in the Safety Population, the ITT Population, and the PP Population, respectively.

The number and percent of subjects who completed or discontinued the study will be displayed for each dose group and overall for subjects on an active NasoVAX dose together with reasons for early termination, where the percent is with respect to the total number of treated subjects in that dose group.

Vaccination administration data will be listed.

8.2 Demographics and Baseline Characteristics

ALT-103-201 and ALT-FLZ-401 subject demographic data and baseline characteristics will be summarized descriptively by dose group and overall for all ALT-103-201 subjects (i.e., subjects on an active NasoVAX dose and placebo). The demographic data and baseline characteristics will be summarized for the Safety, ITT, and PP Populations.

Medical/surgery history will be summarized by SOC and PT for each dose group for ALT-103-201 only. Within each level of summarization, subjects will be counted only once if they had more than one event reported. Medical/surgery history will be summarized for the Safety Population.

8.3 Protocol Deviations

Major protocol deviations for ALT-103-201 subjects, as determined by a sponsor-blinded review of the data prior to database lock and unblinding of the study, may result in the removal of a subject's data from the Per-protocol Population.

All protocol deviations will be presented in a data listing, with a flag to indicate if a violation resulted in the exclusion of the subject from the Per-protocol Population.

Protocol deviations were not collected for subjects in the ALT-FLZ-401 study.

8.4 Prior and Concomitant Medications

Prior and concomitant medications are defined in [Section 7.4.5](#). The number and percentages of all concomitant medications for ALT-103-201 and ALT-FLZ-401 subjects will be summarized by dose group and overall for subjects on an active NasoVAX dose, Anatomical Therapeutic Chemical (ATC) level 3 and PT. If a medication has no ATC Level 3 code, then ATC Level 2 will be used instead. The total number of concomitant medications and the number and percentages of subjects with at least 1 concomitant medication will be summarized by dose group for the Safety Population.

Concomitant medications that were started prior to study treatment will be summarized similarly. Prior medications that are not concomitant will be listed but not tabulated.

8.5 Safety Analysis

All safety analyses will be conducted on the Safety Population, and will be performed for ALT-103-201 only. Summaries will be completed by dose group and overall for subjects on an active NasoVAX dose.

8.5.1 Reactogenicity

Each ALT-103-201 subject will be provided with a diary and a thermometer after each dose. The subjects will record and provide severity grades (Grade 1 – 4) for the following items in a diary daily for the first 14 days after vaccination.

- Local events: nasal irritation, sneezing, nasal congestion, cough, sore throat, change in smell, change in taste, change in vision, eye pain
- Systemic events: headache, fatigue, muscle ache, nausea, vomiting, diarrhea, chills, oral temperature

Oral temperature will be converted to a severity grade using the FDA toxicity grading scale [1].

A cumulative summary of the number and percentage of subjects experiencing at least one reactogenicity event within 14 days after vaccination for each symptom type (local, systemic, temperature, and overall) will be tabulated by maximum severity and dose group. Differences between each NasoVAX dose group and placebo for cumulative symptoms (local, systemic, and overall) will be tested using Kruskal-Wallis tests. The number and percentage of subjects experiencing at least one Grade 3 or 4 reactogenicity event within 14 days after vaccination for each symptom type, as well as 95% Clopper-Pearson exact CIs, will be presented by dose group.

A summary of the number and percentage of subjects experiencing at least one reactogenicity event within 14 days after vaccination will also be tabulated by event

type, maximum severity, and dose group. In addition, a descriptive summary of the duration of symptoms (regardless of severity) will be tabulated by event and dose group.

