6.4 Safety Variables

Safety assessments, some of which are listed as endpoints, include the following:

- Reactogenicity (local events, systemic events, and oral temperature)
- AEs and SAEs (events not already included in reactogenicity)
- Safety laboratory tests (hematology, serum chemistry, urinalysis)
- Vital signs (blood pressure, heart rate, body temperature)
- ECG
- Nasopharyngeal swabs for vector shedding
- Viral culture
- Concomitant medications
- Physical exam

7 Statistical Methodology

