7.4.6 Data Handling

Generally, reactogenicity events recorded in the Subject Diary and (unsolicited) AEs recorded in the AE log will be summarized separately. A reactogenicity event will not be recorded as an (unsolicited) AE unless it meets the criteria of an SAE. Any event found in the AE log that is also captured in the Subject Diary will not be counted as an AE to avoid duplication.

Unscheduled or repeated laboratory results will not be analyzed for the summary of continuous values but may be included in the lab shift tables (see Section 8.5.3). Repeated tests will be included only if they reflect abnormal (low or high) results and the corresponding original results are normal. Repeat vital signs will not be analyzed for the summary of continuous values.

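### SAP 8.5.1 and 7.4.6 have no rule for a solicited symptom still present when the 14-day diary ends: its duration may be capped, and non-serious persistence has no place in any table

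*SAP*

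**What the plan says.** The point concerns the NasoVAX study (ALT-103-201). SAP 8.5 restricts safety analyses to it, and the Fluzone study has no diary.

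- **Collection.** SAP Section 4: "Each subject will record local events, systemic events, and oral temperature in a diary daily for 14 days after the NasoVAX/placebo dose". SAP 8.5.1 repeats the 14-day period. The solicited list includes nasal symptoms and changes in smell, taste and vision. In Table 4-2 the last diary review is the Day 15 visit.
- **Duration.** SAP 8.5.1: "a descriptive summary of the duration of symptoms (regardless of severity) will be tabulated by event and dose group". This is Table 14.3.1.3.
- **Separation from AEs.** SAP 7.4.6: "A reactogenicity event will not be recorded as an (unsolicited) AE unless it meets the criteria of an SAE". It continues: "Any event found in the AE log that is also captured in the Subject Diary will not be counted as an AE to avoid duplication". SAP 6.4 describes the AE variable in the same way: "AEs and SAEs (events not already included in reactogenicity").
- **Later safety collection.** SAP Section 4: "All AEs and medications will be recorded from signing of the informed consent form to Day 29". After that: "Thereafter to the end of the study, only MAEs, NCIs, SAEs, immunosuppressive medications" and vaccines. SAP Section 3 makes AEs to Day 29, and MAEs, SAEs and NCIs to Day 181, part of the primary endpoint.
- **Missing data.** The date conventions in SAP 7.4.8 cover AEs and concomitant medications. They do not cover diary symptoms, and there is no censoring rule.

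**The concern.** A symptom present on the last diary day has not been seen to end. The plan tabulates its duration but does not say whether the value stops at the diary, continues to a later stop date, or is treated as incomplete. The same symptom is also kept out of the AE tables unless it is serious. The two rules meet at the same case: the symptom that lasts.

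For an intranasal product, a lasting nasal or sensory symptom is what a duration table is most useful for showing. If values are cut at diary end, the cut falls hardest on the longest symptoms. A dose group with more persistence would then look closer to the others than it is. The MAE and NCI tables might be expected to catch persistence, but the wording of the duplicate rule puts that in doubt.

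**Working it through.** **The plan's own figure.** The SAP gives no number for symptom duration or persistence. Its only safety calculation (SAP 7.1) is an 80% chance of seeing at least one AE with a true rate of 3.6% in 45 NasoVAX subjects. It reproduces: 1 - (1 - 0.036)^45 = 0.808. The present point does not depend on it.

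**Step 1: cap on duration if only diary days are used.** With diary days 1 to 14 and onset on day d, the most that can be recorded is 14 - d + 1 = 15 - d days.

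| Onset day | Longest recordable duration (days) |
|---|---|
| 1 | 14 |
| 3 | 12 |
| 8 | 7 |
| 10 | 5 |
| 14 | 1 |

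**Step 2: effect on a mean (illustration).** The documents give no duration distribution. Assume geometric durations with true mean m and onset on diary day 3, so the cap is c = 12. With q = 1 - 1/m, the mean recorded duration is m(1 - q^c) and the proportion cut short is q^c.

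| True mean (days) | Mean recorded (days) | Proportion cut short |
|---|---|---|
| 3 | 2.98 | 0.8% |
| 7 | 5.90 | 16% |
| 14 | 8.25 | 41% |
| 21 | 9.31 | 56% |

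Short symptoms are hardly affected. Two groups with true means of 7 and 14 days differ by 7 days, but would show 8.25 - 5.90 = 2.35 days. The difference shrinks but does not vanish.

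**Step 3: how likely the case is to arise (illustration).** Assume that 2% to 10% of subjects have some symptom ongoing at diary end. The chance of at least one such subject is 1 - (1 - p)^n:

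- n = 15 (one dose group): 26% at 2%, 79% at 10%.
- n = 45 (all NasoVAX): 60% at 2%, 99% at 10%.

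**Step 4: trace one symptom through the tables.** Take a non-serious change in smell that starts in the diary period and continues past it.

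- *14-day reactogenicity (Tables 14.3.1.1 and 14.3.1.2):* counted, at its maximum severity.
- *Duration (Table 14.3.1.3):* included, with an undefined value.
- *AE tables:* the first rule in SAP 7.4.6 says it is not recorded as an AE. If it is in the log anyway, the second rule says it is not counted.
- *MAE and NCI tables (14.3.2.7 and 14.3.2.8):* SAP 8.5.2 promises summaries of these events. The duplicate rule applies to any AE-log event also captured in the diary and names no exception. The first rule excepts SAEs only, and the second does not repeat even that.

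No table is assigned to the non-serious continuation. If it becomes an MAE or NCI, SAP 7.4.6 and 8.5.2 give different answers.

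**The case against.** A reader might infer that a lasting symptom disappears from the safety results. The documents do not support that. Any diary symptom within 14 days is counted by event type and maximum severity, Grade 3 or 4 events are also summarised by symptom type with exact intervals, and all collected data are listed. Only the continuation lacks a table.

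A reader might also take it as settled that durations are truncated. That too is an inference. The SAP does not define duration, and the ALT-103-201 protocol, the eCRF and the table shells were not available for this review. Any of them might provide for a stop date collected at Day 15 or Day 29.

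The primary reactogenicity endpoint counts subjects with events over 14 days, so truncation leaves it unchanged. Duration is a descriptive table without a test. The duplicate rule follows an opening qualified as general and is meant to prevent double counting, so a continuation after Day 14 might be read as outside it. Finally, requiring every ongoing symptom to be entered in the AE log would change data collection and blur the intended split between solicited and unsolicited events.

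These objections limit the claim and rule out that last remedy. They do not supply the missing rule. A listing is not a comparison by dose group and shows only what was recorded. If stop dates exist, SAP 8.5.1 does not say to use them. The ambiguity over MAEs and NCIs affects primary counts, not just the duration table.

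**Conclusion.** The concern holds in limited form. The SAP has no rule for solicited symptoms ongoing at diary end. Non-serious persistence after the diary has no stated place in any table. Read literally, the duplicate rule in SAP 7.4.6 would remove a diary-onset MAE or NCI from primary counts that run to Day 181.

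The cap of 15-d days is exact if duration is taken from diary days, which the SAP leaves open. The bias is negligible if symptoms are short and material if they last one to three weeks, under assumed durations. The number of subjects affected cannot be derived from the documents. It would be too strong to say that dose-related persistence is hidden, since a difference would be reduced but not erased. This is a reporting gap worth closing before the final analysis. It does not undermine the 14-day incidence results.

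**What to change.** 1. **SAP 8.5.1 and Table 14.3.1.3.** Define duration. For each symptom, show by dose group the number and percent of subjects in whom it was present on the last diary day. Where a stop date was collected, use it. Otherwise treat the duration as censored at diary end and mark it so in the summary, not as a completed episode.
2. **SAP 7.4.6.** State that the duplicate rule does not remove SAEs, MAEs, NCIs or AE-log entries that document continuation beyond the diary. Show those continuations on a separate line, so that solicited and unsolicited events stay distinct.

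**Cost.** SAP wording, one extra table row and a few more counted events. The last-day diary entries are already collected, AE assessment already runs to Day 29, and MAE, NCI and SAE assessment to Day 181. No new data collection is needed, because the change governs only how existing entries are counted and shown.
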